#### **Other Exclusions**

- 21. Participant is pregnant (as indicated by a positive urine pregnancy test assessed at Screening and before each TRP-8802 session) or nursing.
- 22. Participant is a WOCBP and sexually active, or a man and sexually active, and not practicing an effective means of birth control.
- 23. Participant has a confirmed first- or second-degree relative with schizophrenia spectrum or other psychotic disorders (except substance/medication-induced or due to another medical condition), or bipolar I or II disorder.

# **5.3.** Lifestyle Considerations

Some lifestyle considerations (e.g., diet, smoking habits, alcohol, or recreational drug consumption) could be of relevance for this study. Therefore, the following restrictions apply:

- Caffeine-containing beverages are allowed during the study, including on TRP-8802 session days. However, participants are expected to consume approximately the same amount of caffeine-containing beverages that they usually consume before arriving at the research unit on the mornings of TRP-8802 drug sessions.
- Participants must be non-smokers (tobacco) before and during the entire study.
- Psychoactive drugs, including prescription and recreational drugs, are only allowed during the study period as described in the study protocol.
- Alcoholic beverages and psychoactive drugs are not allowed within 24 hours before and after each TRP-8802 administration.
- For 7 days before each TRP-8802 session, participants must refrain from taking any nonprescription medication, nutritional supplement, or herbal supplement except when approved by the Principal Investigator. Exceptions must be evaluated by the Principal

CONFIDENTIAL 32 27 February, 2024

Investigator and may include acetaminophen, non-steroidal anti-inflammatory drugs, and common doses of vitamins and minerals. No PRN medications are allowed on the mornings of TRP-8802 administration.

• Drugs such as sildenafil (Viagra®), tadalafil, or similar medications are not allowed within 72 hours before and after each TRP-8802 administration.

There are no restrictions on physical activity during the study. TRP-8802 session days will be held under the supervision of two therapists who are present throughout the session. Sessions will be conducted in a room designed to be quiet, comfortable, and aesthetically pleasing, and participants are encouraged to wear eyeshades and listen to a program of music through headphones during the drug exposure to aid them in focusing their attention inward.

Participants should agree to not drive or operate machinery on the day of TRP-8802 administration. Participants must agree to be driven home after TRP-8802 drug sessions. Once they are considered to be medically stable post-dose by the Investigator, participants will be discharged and should accompanied for the evening by a family member or caregiver.

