#### 4.1.4. TRP-8802 Administration Period (Visit 5 to Visit 9, Day 22 to Day 37)

The procedures used during the administration period will be consistent with those from other published studies using psilocybin assisted therapy (Davis 2021a). Participants will be asked to eat a low-fat breakfast before reporting to the Rachel Upjohn Building for their dosing sessions. Before administration of study drug, participants will provide urine samples that will be tested for drugs (Section 8.3.3) as well as for pregnancy for WOCBP (Section 8.3.2); tested for COVID-19; and a breath alcohol test will also be administered (Section 8.3.3). All tests must be negative for participants to proceed. Participants will also complete pre-session questionnaires and a brief interview with study personnel. The purpose of this brief interview is to assess if the session is contraindicated. If so, then that session will be postponed if possible.

Participants will receive an initial 15 mg dose of TRP-8802 (lower dose) on Day 22 followed by the second dose of 25 mg (higher dose) on Day 36. TRP-8802 will be administered in a comfortable setting under the guidance of the same two therapists from the preparation period. The 15 mg dose can be repeated at Dose 2 if the participant or Investigator determines that the higher dose is not advantageous and/or may not provide further benefit, based on observations for Dose 1. Participants will have an in-person study visit the day after each dose administration (Day 23 and Day 37) to ensure participant safety and comfort. There will also be a visit (virtual using a HIPAA-compliant video conferencing platform or in-person) 7 days after administration of the first dose (Day 29) to integrate the first experience and prepare the second dosing day.

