#### 6.1.1. TRP-8802 Administration

Participants will be instructed to consume a light, low-fat breakfast before TRP-8802 administration. Capsules of TRP-8802 will be administered orally with 8 ounces of water at the research unit under the supervision of study staff. Capsules should not be opened or chewed. The drug session will be rescheduled if a friend or family member of the participant is not available to accompany them home after being discharged from the research unit.

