#### 6.1.2. Leaving the Research Unit

Participants will not be allowed to leave the research until the study staff makes the judgment that the effects of the study intervention have completely subsided. Participants will expected to be on the research site for at least 8 hours. The discharge criteria are as follows (all of the following must be met):

• A responsible friend/family member is available to accompany the participant home.

CONFIDENTIAL 35 27 February, 2024

• The participant's clinical status is not deemed to be of concern by the clinical judgment of a study physician.

- The participant is deemed by study staff to be free of any acute drug effects.
- The participant believes they have approximately returned to their psychological baseline.
- The study staff judges that it is safe to discharge the participant.
- The participant expresses a readiness to go home.

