# 8.5. Clinical Safety and Monitoring

At enrollment, potential participants will be appropriately screened for exclusionary psychiatric conditions, medical co-morbidities, and concomitant medications. In addition medical screening will include blood tests including complete blood count (CBC), comprehensive metabolic panel (CMP), urine drug screen (UDS). Subjects with any clinically significant lab abnormalities will be excluded from participation.

Throughout the entire study, suicidal ideation will be assessed during every in-person visit using the C-SSRS and clinical assessment during participant interviews. Significant suicidal ideation is endorsed on items 4 or 5 on the C-SSRS. If the patient screens positive on the C-SSRS at any time during the study, they will undergo a more detailed suicidal risk assessment by study clinician. If they are determined to be at risk of suicide they will be transferred to ED for further Psychiatric evaluation.

During administration, heart rate and BP will be assessed before TRP-8802 capsule administration and at 30, 60, 90, 120, 180, 240, 300, and 360 minutes after capsule administration. Blood pressure and pulse measurements should be preceded by at least 5 minutes of rest for the participant in a quiet setting without distractions (e.g., television, cell phones). If a patient's blood pressure is >200 systolic or >110 diastolic for more than 15 minutes (i.e. 4 consecutive readings) they will be transferred to ED whether or not they are symptomatic.

AEs will be monitored at every study visit. Study staff will also be available throughout the course of the study for emergent AEs. Throughout the administration period, therapists will assess the presence and intensity of participant behaviors, symptoms, and non-verbal cues, which includes questions about the presence/intensity of behaviors, signs, and reported symptoms, such as peacefulness, yawning, nausea/vomiting, quantity of speech, anxiety, sleepiness, crying, restlessness, visual changes, euphoria, and feelings of unreality. They will also complete assessments of mood and safety at the end of the administration sessions.

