The session therapists are trained to reassure the participants if they experience acute anxiety, agitation, paranoia, or panic. However, in the unlikely event that those symptoms do not respond to reassurance, or if a participant experiences a severe AE outside of the expected challenging experiences associated with psilocybin therapy, one of the session therapists will contact the on-call study physician. The study physician will use their clinical judgment to determine the most appropriate medical intervention. There will be an automated external defibrillator located on site and a crash cart containing medicine and equipment for emergency resuscitation, including rescue medication as described in section 6.8.1. After dosing sessions, participants will be discharged only if they meet all criteria in section 6.1.2., including being accompanied home by a responsible friend or family member.

During the post-dosing period (visits 6, 7, 9, 10), monitors will also complete assessments of participant mood and safety after therapy visits.

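### Section 5.3 asks for company on the evening after each dose, but the rescheduling rule and the discharge list check only for someone to accompany the participant home (minor)

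*Combined protocol and SAP*

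**What the plan says.** Section 5.3 (Lifestyle Considerations) deals with the hours after a dose in two steps. Participants must agree to be driven home. After that, "participants will be discharged and should accompanied for the evening by a family member or caregiver". This is the only place in the document that mentions company for the evening.

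Three other places deal with a companion:

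- Section 6.1.1, before dosing: "The drug session will be rescheduled if a friend or family member of the participant is not available to accompany them home" after discharge.
- Section 6.1.2, at discharge. This is a list of six criteria, all of which must be met. The first reads "A responsible friend/family member is available to accompany the participant home".
- Section 8.5, which points back to that list: "participants will be discharged only if they meet all criteria in section 6.1.2., including being accompanied home by a responsible friend or family member".

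Section 6.1.2 contains other protections. Nobody leaves until staff consider the drug effects to be fully over, and a stay of at least 8 hours is expected. The remaining criteria cover the physician's view of clinical status, freedom from acute effects, the participant's own view ("The participant believes they have approximately returned to their psychological baseline"), staff judgment that discharge is safe, and the participant's readiness to go. Section 8.5 adds that "Study staff will also be available throughout the course of the study for emergent AEs", and Section 4.1.4 that "Participants will have an in-person study visit the day after each dose administration (Day 23 and Day 37) to ensure participant safety and comfort".

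**The concern.** The protocol names evening company as a precaution after a psychoactive dose, but the rules that staff apply on the day do not ask about it. Someone who lives alone could be taken home by a friend, satisfy every written condition and then spend the evening alone. Being taken home and having company afterwards are separate steps in 5.3, so meeting the first does not meet the second. A precaution missing from the discharge list depends on staff or participants remembering it.

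What is at stake is participant safety and comfort between discharge and the next-day visit, a period with no scheduled contact. The gap itself does not affect the statistical analyses.

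**Working it through.** The protocol gives no figure to reproduce, so the check is a comparison of sections, followed by simple date arithmetic for the fix.

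**Comparison of sections**

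| Section | When it applies | Who | Covers the trip home | Covers the evening | Force |
|---|---|---|---|---|---|
| 5.3 | after discharge | family member or caregiver | yes (driven home) | yes | must for the drive, should for the evening |
| 6.1.1 | before dosing | friend or family member | yes | no | session rescheduled if not met |
| 6.1.2, first item | at discharge | responsible friend or family member | yes | no | mandatory |
| 8.5 | restates 6.1.2 | responsible friend or family member | yes | no | mandatory |

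Evening company is named in 0 of the 2 checks that control a session (6.1.1 and 6.1.2; 8.5 only repeats the latter) and in 0 of the 6 discharge criteria. The permitted companion also differs. A friend satisfies 6.1.1 and 6.1.2 but is not named in 5.3 unless regarded as a caregiver.

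**Other places that might supply the check**

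- Section 4.1.4 sets the other pre-dose conditions: negative drug, pregnancy, COVID-19 and alcohol tests, and a short interview about whether the session is contraindicated. None names a companion.
- Inclusion criterion 14 (Section 5.1) binds participants through consent to the protocol's requirements, and Section 8 calls for adherence to the study design. Neither confirms a companion on the day.

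**Scale**

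10 participants × 2 doses = 20 dosing evenings. The documents give no basis for estimating how many would be spent alone.

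**Timing of a confirmation** (days and windows from the Schedule of Activities, Section 1.3)

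- Dose 1: Day 22 ± 3 = Days 19 to 25. Dose 2: Day 36 ± 3 = Days 33 to 39.
- Visit 3: nominal lead 22 − 11 = 11 days. Window 11 ± 7 = Days 4 to 18, which ends before the Dose 1 window opens.
- Visit 4: nominal lead 22 − 18 = 4 days. Window 18 ± 7 = Days 11 to 25, which can run past the nominal Dose 1 day, so the 4-day lead is not assured.
- Visit 7: nominal lead 36 − 29 = 7 days. Window 29 ± 3 = Days 26 to 32, which ends before the Dose 2 window opens.

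Preparation visits alone therefore do not guarantee a late check before Dose 1. A further confirmation on the dosing day is needed.

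**The case against.** The strongest reply is that nothing is inconsistent. Section 5.3 requires the drive home and recommends the evening company, and only the requirement is enforced. Other post-discharge instructions in 5.3, such as no alcohol for 24 hours and no driving that day, are not discharge criteria either. An escort described as responsible may be meant to do more than provide transport. Staff must consider discharge safe and can take home circumstances into account. The expected stay of at least 8 hours is about 2.7 half-lives of psilocin at the 3 hours given in Section 4.3 (8 / 3 = 2.7), so evening company is not the main safety control. The Psychotherapy Manual, to which Section 4.1 refers for session details, or the consent form may already cover it.

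Much of this stands, and it keeps the point minor. It does not remove it. Unlike abstinence from alcohol, a companion can be confirmed in advance, and 6.1.1 already makes a session depend on one. Neither 6.1.1 nor 6.1.2 says that the escort stays, and discretion to ask about the evening is not a check that someone has asked.

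A reader might infer more: that the sections contradict each other, that participants are discharged unsafely, or that the efficacy results are at risk. The documents do not support these readings. The word should in 5.3 rules out a contradiction, the safeguards in 6.1.2 and the next-day visit limit the hazard, and the gap does not touch any analysis.

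**Conclusion.** The point holds as a minor gap in enforcement. Section 5.3 states a precaution that neither the rescheduling rule nor the discharge list checks, so the protocol as written allows dosing and discharge with no evening companion arranged. It applies to about 20 dosing evenings if 10 participants receive both doses. The remaining risk is small, and no event rate can be given.

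The conclusion rests on two assumptions: that the sponsor means the evening company in 5.3 to be provided, and that accompanying someone home does not by itself include staying. It covers this document only. If the Psychotherapy Manual or consent form has a companion check, what remains is a need to align the wording.

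**What to change.** Change the first item of 6.1.2 to: *a responsible adult (family member, friend or caregiver) is available to accompany the participant home and stay with them for the evening.* Use the same condition in the rescheduling rule of 6.1.1 and in 8.5, and align 5.3 to it, which also supplies its missing verb.

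Confirm the companion at Visits 3 and 4 for Dose 1 and at Visit 7 for Dose 2. Visit 7 suits this because it takes place "7 days after administration of the first dose (Day 29) to integrate the first experience and prepare the second dosing day". Confirm again before the capsules are given, for example in the pre-session interview of 4.1.4, because the Visit 4 window can run past Dose 1.

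The cost is wording in four sections and one question at contacts that already take place. Participants who live alone must arrange company for two evenings. An occasional session may have to move within its ± 3 day window. A Dose 2 that cannot be rescheduled would take that participant out of the Full Analysis Set, which requires both doses (Section 9.3, Table 7). The goal in Sections 1.1 and 9.2 is about 10 participants who complete both doses, so the main consequence would be recruiting one more, and it would be wrong to count it as a loss of 1 in 10 from a fixed sample. Early confirmation is meant to keep this rare.

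If the sponsor intends evening company only as advice, 5.3 should say so plainly.

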#### 5.4. Screen Failures

Screen failures are defined as participants who consent to participate in the clinical study but are not subsequently entered in the study. A minimal set of screen failure information is required to ensure transparent reporting of screen failure participants to meet the Consolidated Standards of Reporting Trials (CONSORT) publishing requirements and to respond to queries from regulatory authorities. Minimal information includes demography, screen failure details, eligibility criteria, and any SAE.

Individuals who do not meet the criteria for participation in this study (screen failure) may be rescreened. If a participant is taking an exclusionary medication at screening, and the participant and their health care provider(s) agree that it is appropriate to change medication(s), then rescreening may occur after the appropriate washout period.

Rescreened participants should be assigned a new participant number for every screening/rescreening event.

# 5.5. Criteria for Temporarily Delaying Enrollment or Administration of Study Intervention

If any of the stopping rules below is met, dosing will pause until the SRC convenes (either routine or ad hoc) to review details of the event and/or additional data. If, after further review of the data, the SRC determines that no stopping rule has been met (e.g., AE determined to be unrelated to the study drug) or that if a stopping rule has been met there is a way to safely continue the trial (e.g., appropriate safety monitoring can be implemented), then dosing may resume. The occurrence of any of the following events will result in a temporary halt of dosing:

- one SAE considered at least possibly related to the study drug
- one Grade 3 or Grade 4 AE considered at least possibly related to the study drug
- clinically similar Grade 2 AEs considered at least possibly related to the study drug in 2 participants

CONFIDENTIAL 33 27 February, 2024

The study may be discontinued at any time by the Institutional Review Board (IRB), the FDA, or other government agencies as part of their duties to ensure that research participants are protected.

CONFIDENTIAL 34 27 February, 2024

## 6. Study Intervention(s) and Concomitant Therapy

In this protocol, study intervention is the combination of the investigational TRP-8802 and psychotherapy. This Section covers the administration of TRP-8802; psychotherapy treatment is covered in more detail in the Psychotherapy Manual.

## 6.1. Study Intervention TRP-8802

TRP-8802 intervention, doses, and route of administration are presented in Table 4.

**Table 4: Study Treatments Administered** 

| Intervention Name          | TRP-8802  |
|----------------------------|---|
| Type                       | Drug  |
| Dose Formulation           | Capsule   |
| Unit Dose Strengths | 5 mg and 25 mg  |
| Dosage Levels              | 15 mg (3 x 5 mg) and 25 mg (1 x 25 mg)  |
| Route of Administration    | Oral  |
| Use                        | Experimental  |
| Sourcing                   | Provided centrally by the Sponsor   |
| Packaging and Labeling     | TRP-8802 will be provided in high-density polyethylene bottles. Each bottle will be labeled in accordance with appropriate regulatory requirements. |
| Current/Former Name        | Psilocybin  |
| Manufacturer               | Usona Institute   |

#### 6.1.1. TRP-8802 Administration

Participants will be instructed to consume a light, low-fat breakfast before TRP-8802 administration. Capsules of TRP-8802 will be administered orally with 8 ounces of water at the research unit under the supervision of study staff. Capsules should not be opened or chewed. The drug session will be rescheduled if a friend or family member of the participant is not available to accompany them home after being discharged from the research unit.

#### 6.1.2. Leaving the Research Unit

Participants will not be allowed to leave the research until the study staff makes the judgment that the effects of the study intervention have completely subsided. Participants will expected to be on the research site for at least 8 hours. The discharge criteria are as follows (all of the following must be met):

• A responsible friend/family member is available to accompany the participant home.

CONFIDENTIAL 35 27 February, 2024

• The participant's clinical status is not deemed to be of concern by the clinical judgment of a study physician.

- The participant is deemed by study staff to be free of any acute drug effects.
- The participant believes they have approximately returned to their psychological baseline.
- The study staff judges that it is safe to discharge the participant.
- The participant expresses a readiness to go home.

## 6.2. Preparation/Handling/Storage/Accountability

- The investigator or designee must confirm appropriate temperature conditions of 15°C to 25°C have been maintained during transit for all study intervention received and any discrepancies are reported and resolved before use of the study intervention.
- The investigator or designee must confirm appropriate temperature conditions of 15°C to 25°C have been maintained at the study site for all study intervention and any discrepancies are reported and resolved before use of the study intervention.
- Only participants enrolled in the study may receive study intervention and only
  authorized site staff may supply or administer study intervention. All study intervention
  must be stored in a secure, environmentally controlled, and monitored (manual or
  automated) area in accordance with the labeled storage conditions with access limited to
  the investigator and authorized site staff.
- The investigator is responsible for study intervention accountability, reconciliation, and record maintenance (i.e., receipt, reconciliation, and final disposition records).
- Further guidance including information for the final disposition of unused study interventions are provided in the Pharmacy Manual.

